2.9 Main outcome variables

Dependent variable

Pre-eclampsia

Independent variables

- Age
- Parity
- BMI
- Educational status
- Monthly income
- Occupation
- Blood pressure
- Proteinuria
- Aspirin

2.10 Operational definitions:

Hypertension: According to ACOG hypertension is defined as: BP equal to or greater than 140/90 mm of Hg, rise of systolic BP 30 mm of Hg or rise of diastolic BP 15 mm of Hg or more. (Arias“ 2015)

Chronic HTN: Hypertension that was present before pregnancy or it was diagnosed before 20th week of gestation.

Internationally agreed definition of PE is that of the International Society for the Study of Hypertension in Pregnancy (ISSHP) which is endorsed by FIGO.

Gestational hypertension: is defined as systolic blood pressure (sBP) at ≥ 140 mm Hg and/or diastolic blood pressure (dbp) at ≥ 90 mm Hg on at least two occasions measured 4 hours apart developing after 20 weeks of gestation in previously normotensive women.

Preeclampsia: is defined as gestational hypertension accompanied by ≥ 1 of the following new-onset conditions at or after 20 weeks of gestation:

1. Proteinuria (i.e. ≥ 30 mg/mol protein:creatinine ratio; ≥ 300 mg/l in 24 hour; or $\geq 2+$ dipstick)

2. Other maternal organ dysfunction:

Acute kidney injury (creatinine ≥ 90 $\mu\text{mol/L}$; 1 mg/dL)

Liver involvement (elevated alanine aminotransferase or aspartate aminotransferase >40 IU/L) with or without right upper quadrant or epigastric pain)

Neurological complications (including eclampsia, altered mental status, blindness, stroke, or more commonly hyperreflexia when accompanied by clonus, severe headaches, and persistent visual scotomata)

Hematological complications (thrombocytopenia—platelet count $<150\ 000/\mu\text{L}$, disseminated intravascular coagulation, hemolysis) or

3. Uteroplacental dysfunction (fetal growth restriction, abnormal umbilical artery Doppler waveform or stillbirth).

Superimposed PE on chronic hypertension:

- Women with chronic essential hypertension develop any of the above maternal organ dysfunctions consistent with PE
- Increase in blood pressure per se is not sufficient to diagnose superimposed PE
- In the absence of pre-existing proteinuria, new-onset proteinuria in the setting of a rise in blood pressure is sufficient to diagnose superimposed PE.

2.11 Research instruments

Structured questionnaire will be prepared for this purpose, which will include all the variables of interests.

2.12 Data collection technique

a) Interviewing for risk factor evaluation

b) Examination including-

- Blood pressure measurement

- Height ,Weight & BMI

c) Investigation Reports

Measurement of blood pressure : After 10 minutes rest, BP will be measured following standard procedure. Korotkoff phase 1(first beat heard) an phase V (disappearance of sound) will be used to determine systolic (SBP) and diastolic blood pressure (DBP) (Hendler et al., 2005).

Measurement of proteinuria: Proteinuria is measured by dipstick test at least two midstream urine samples 6 hrs apart, in the absence of urinary tract infection. Test for

protein in urine by multiple reagent strip (dipstick) as follows: Trace = 0.1 gm/L; 1+ = 0.3 gm/L; 2+ = 1.0 gm/L; 3+ = 3.0 gm/L; 4+ = 10.0 gm/L (Haugen et al., 2006).

2.13 Data presentation and analysis plan

- Statistical analyses will be carried out by using Windows based Statistical Package for Social Sciences (SPSS-22.0).
- For continuous variables, distributions will be expressed by mean and standard deviation. Mean comparisons between two groups will be done by student's t-test.
- For qualitative variables, distributions will be expressed by frequency and their percentages. Chi square tests will be done to see the significance of differences between two groups.
- Relative Risk (RR) and 95% confidence interval will also be estimated for the outcome.
- The p value <0.05 will be declared as statistically significant.

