1.4 Objectives

General objective

- To find out the effect of low dose aspirin in prevention of preeclampsia among pregnant women who are at high risk for developing preeclampsia.

Specific objectives

- To find out the socio-demographic characteristics (Age, Occupation,
- To find out the primary outcome (occurrence of Preeclampsia) among both intervention & control group.
- To detect the secondary outcome among both groups: Maternal- Gestational HTN, Oligohydramnios, Preterm labor, Placental abruption, APH, PPH ; Fetal- LBW, Preterm birth , Small for gestational age, IUD,Still Birth, NICU admission among both groups.
- To compare the outcome of two groups.
- To analyze the possible association between Aspirin & Pre-eclampsia.

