$p_2 = 8.71\%$ [Incidence of preeclampsia high risk group(Poon L.C et.al., 2019)]

$$p = \frac{p_1 + p_2}{2} = \frac{0.016 + 0.0871}{2} = 5.155\%$$

$Z_{\alpha} = 1.96$ at a 95% confidence interval

$Z_{\beta} = 0.84$ at a 80% power

Putting the values in the above equation the sample size n is estimates as

$$n = \left[\frac{1.96 \sqrt{0.016(1-0.016)} + 0.84 \sqrt{0.0871(1-0.0871)}}{0.0871 - 0.016} \right]^2 = 150.30 \approx 150$$

According to sample size determination it will be 150 in each group but 100 sample size in each group will be taken due to limitation of time.

2.8 Selection Criteria-Pregnant women have to fulfill any 1 of the following criteria to enroll the study

Inclusion criteria for both groups:

- Maternal age ≥ 18 years
- Advanced maternal age (≥ 35 years)
- BMI ≥ 30 kg/m²
- Live foetus at gestational age 12 weeks - 19 weeks.
- Pregnancy interval >10 years.
- Multiple pregnancy.
- Pregnancy assisted by Ovulation inducing drugs/ In vitro fertilization.
- Pregnant women with medical disorders-Chronic HTN,Hyperglycaemia in pregnancy,Thyroid disorder ,Autoimmune disease-APS,SLE.
- Previous history of Gestational HTN,PE, Eclampsia
- Previous history of IUGR, IUD, Still Birth.
- Family history of HTN, Gestational HTN, PE (mother and/or sister)

Exclusion criteria for both groups:

- Allergic to Aspirin.
- Peptic ulcer disease.
- Mental disease.
- Patient with treatment of antifolate drugs (antiepileptics, methotrexate)
- Patient who will not give consent to participate.

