2.15 Sample Table

Table 1 : Socio demographic characteristics of study population (N=)

Characterstics	Intervention		Control		P value
	n=	n%	n=	n%	
Age					
≤18 years					
19-34years					
≥ 35 yrs					
Parity					
Nulliparous					
Multipara					

Socio demographic characteristics of study population (N=)

Educational status			
Illiterate			
Primary SSC			
HSC and above			
Occupation			
Housewife			
Service holder			
Others			
Monthly income (tk)			
<10,000			
(10,000-20,000)			
(20,000-40,000)			
>40,000			

Table 2: Distribution of study groups by BMI (kg/m²) (N=)

BMI (KG/ m ²)	Intervention		Control		P value
	n =	n%	n =	n%	
<18.5 (underweight)					
18.5-24.9 (normal)					
25-29.9 (overweight)					
30-39.9 (obese)					
Mean ± SD					

P value will be reached from chi square test.

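### Section 2.13 declares any p<0.05 significant without limiting this to pre-eclampsia, so each of 12 secondary outcomes can be claimed as a finding (minor; the primary test is unaffected)

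*Protocol*

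**What the plan says.** Section 1.4 names one primary outcome: "To find out the primary outcome (occurrence of Preeclampsia) among both intervention & control group". It then lists six maternal secondary outcomes, "Maternal- Gestational HTN, Oligohydramnios, Preterm labor, Placental abruption, APH, PPH", and six fetal ones: low birth weight, preterm birth, small for gestational age, intrauterine death, stillbirth and NICU admission. A further objective is to compare the two groups on outcome. Section 2.6 says that both primary and secondary outcomes will be observed and the groups then compared.

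Section 2.13 gives the test for all categorical variables, "Chi square tests will be done to see the significance of differences between two groups", and ends with the threshold: "The p value <0.05 will be declared as statistically significant". No sentence in the protocol limits that threshold to pre-eclampsia, calls the secondary outcomes exploratory, orders them or adjusts for their number.

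The same threshold reaches the baseline tables in section 2.15. They have a p-value column, and a note reads "P value will be reached from chi square test".

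**The concern.** Taken literally, the rule gives 12 secondary outcomes the same licence to be declared significant as the one outcome the trial was sized for. With that many comparisons at 5% each, a chance finding somewhere in the list is quite likely even if aspirin does nothing.

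The setting makes this more than a formality. Section 2.7 calculates 150 women per group and then takes 100. A non-significant primary result beside a nominally significant secondary one is therefore a realistic outcome, and the rule would let the secondary one be presented as a finding. Errors in both directions matter: section 1.2 says that the safety of the drug will be evaluated, and abruption, APH and PPH bear on safety. A chance excess could be read as harm as easily as a chance deficit could be read as benefit.

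**Working it through.** **Inputs from the protocol**
- Significance level per test: 0.05 (section 2.13). It is two-sided, since the test is chi-square and section 2.7 uses a normal deviate of 1.96.
- Secondary outcomes: 6 maternal + 6 fetal = 12 (section 1.4).
- Planned size: 100 per group; planning rates for pre-eclampsia 1.6% and 8.71% (section 2.7).
- The outcome part of the data collection sheet (section 5) has no field for abruption and puts intrauterine death and stillbirth on one line. About 10 of the 12 can therefore be tested separately.

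**Assumed.** The protocol gives no event rates for the secondary outcomes and no correlations between them.

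**The plan's own figure.** The protocol states no overall error rate. Its only number that depends on the significance level is the sample size of 150.30 per group. The standard pooled two-proportion formula, two-sided 5% and 80% power, gives 150.5, so 150 is reproduced as a calculation for pre-eclampsia alone. (The formula as printed evaluates to 46.1; that is a separate matter.)

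**Step 1: independent tests, no effect of aspirin.** P(at least one false claim) = 1 − 0.95^k.
- k = 12: 1 − 0.95^12 = 1 − 0.540 = 0.460
- k = 10: 1 − 0.95^10 = 1 − 0.599 = 0.401

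These count false claims in either direction. For false benefit only, 1 − 0.975^12 = 0.262.

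**Step 2: rare events.** With few events the chi-square test rejects less often than 5%. Its exact size (no continuity correction) at 100 per group is 0.0135 at a risk of 1%, about 0.044–0.045 at 3–5%, and about 0.051–0.052 at 10–20%. Assume 1% for abruption, intrauterine death and stillbirth, 3% for APH, 5% for PPH and 10–20% for the other seven. Then, still assuming independence:

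1 − (0.9865^3 × 0.9554 × 0.9564 × 0.9485^7) = 1 − 0.606 = 0.394

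**Step 3: overlap.** Abruption is a form of APH; preterm labour, preterm birth, low birth weight and NICU admission go together; intrauterine death and stillbirth overlap. With equally correlated normal test statistics:

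| Correlation | 12 tests | 10 tests |
|---|---|---|
| 0 | 46% | 40% |
| 0.2 | 43% | 38% |
| 0.3 | 40% | 35% |
| 0.5 | 32% | 29% |
| 0.7 | 23% | 21% |

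**Step 4: both together.** Patient-level simulation of 12 binary outcomes at 100 per group, with latent correlation from 0 to 0.5 or a clinical block structure, gave about 41–46% when events were assumed common, 40–43% when moderate and 36–38% when rare.

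**Step 5: the primary outcome.** At 1.6% against 8.71% and 100 per group, exact chi-square power is 64%. If the relative risk of 0.68 from the meta-analysis in section 1.5 is applied to 8.71%, power is about 12%.

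**Step 6: number of false claims under no effect, 12 independent tests.** None: 0.95^12 = 54%. Exactly one: 12 × 0.05 × 0.95^11 = 34%. Exactly two: 66 × 0.05² × 0.95^10 = 10%.

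**The case against.** The strongest reply is that the sentence in section 2.13 merely defines nominal significance. Labelling, ordering or adjusting secondary outcomes is commonly left to a statistical analysis plan, which may exist but is not shown, and unadjusted secondary outcomes are usual in a small single-centre academic trial. Part of this stands: the absence of a multiplicity procedure is not a fault of this protocol. What remains is that the protocol does fix a declaration rule, without qualification, under its analysis-plan heading. A later plan that treated the secondary outcomes as exploratory would have to depart from it.

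A reader might infer that nothing separates the confirmatory comparison from the rest, so that the trial's main conclusion is at risk. The protocol does not support that. The hypothesis (1.3), the primary label (1.4), the sample size (2.7) and the single dependent variable (2.9) all point to pre-eclampsia. With one named primary outcome, its type I error remains 5%.

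A reader might also infer that the most probable result is a null primary with one or two spurious secondary findings. That fails too. At the protocol's own rates the primary test has 64% power, so it is more likely than not to be significant. If aspirin does nothing, no significant secondary outcome is the single most probable result (54% in step 6). Primary power is low only if the true effect is well below the planning assumption, and in that case a significant secondary result need not be false.

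Finally, 46% requires independence, which the overlapping list itself rules out. It is an upper bound and should be labelled so.

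**Conclusion.** The point holds as a wording fault of minor severity. Followed literally, section 2.13 allows any of 12 secondary outcomes, about 10 of them separately recorded, to be declared significant at 5%. If aspirin has no effect, the chance of at least one false secondary claim in either direction is at most 46% (12 independent tests) or 40% (10 independent tests). It is roughly 30–40% once overlap and rare events are allowed for. Very strong correlation would take it lower, and common events with weak correlation would keep it a little above 40%. The range rests on assumed correlations and event rates.

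The baseline p-values in section 2.15 are presentational. They make no efficacy claim and do not add to the severity.

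**What to change.** Replace the last sentence of section 2.13 with: *Statistical significance at two-sided p<0.05 will be declared for pre-eclampsia only; secondary outcomes will be reported as RR with 95% CI and described as exploratory.*

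This needs no new data, patients or analyses, since section 2.13 already plans relative risks with confidence intervals. The downside is that no secondary outcome can be headlined as significant.

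If the investigators want to keep the option of a secondary claim, a Bonferroni threshold of 0.05/12 = 0.0042 would hold the overall chance at 1 − (1 − 0.0042)^12 ≈ 4.9% under independence, at the price of much lower power for each outcome.

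Removing the p-values from the baseline tables is optional.

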2.14 Time table: (Activities with time schedule)

Activities	September- November 2017	December- May2018	1st Three months	2nd Three months	3rd Three months	4th Three months
Phase I Topic selection, Literature search, Protocol writing & submission, Pretesting						
Phase II Data collection & compilation						
Phase III Data entry, edit and analysis						
Phase IV Report writing and submission						

2.15 Sample Table

Table 1 : Socio demographic characteristics of study population (N=)

Characterstics	Intervention		Control		P value
	n=	n%	n=	n%	
Age					
≤18 years					
19-34years					
≥ 35 yrs					
Parity					
Nulliparous					
Multipara					

Socio demographic characteristics of study population (N=)

Educational status			
Illiterate			
Primary SSC			
HSC and above			
Occupation			
Housewife			
Service holder			
Others			
Monthly income (tk)			
<10,000			
(10,000-20,000)			
(20,000-40,000)			
>40,000			

Table 2: Distribution of study groups by BMI (kg/m²) (N=)

BMI (KG/ m ²)	Intervention		Control		P value
	n =	n%	n =	n%	
<18.5 (underweight)					
18.5-24.9 (normal)					
25-29.9 (overweight)					
30-39.9 (obese)					
Mean ± SD					

P value will be reached from chi square test.

2.16 Ethical Consideration

There is minimum physical, psychological, social and legal risk during taking history, physical examination and investigations. Proper safety measures will be taken in every step of the study. Only researcher will be allowed to access the collected data. Ethical clearance will be obtained from Institutional Review Board (IRB) of BIRDEM to undertake the current study. According to Helsinki Declaration for Medical Research involving Human Subjects 1964, all the patients will be informed about the study design, the underlying hypothesis and the right of the participants to withdraw themselves from the research at any time, for any reason. Informed written consent will be obtained from each subject who will voluntarily provide consent to participate in this study.

[figure not shown]
The following ethical issues will be addressed accordingly:

1. Strict confidentiality and security of data related to patient will be maintained. The presentation of data and information related to patient will be documented anonymously.
2. The data analysis will be completed on the subjects who complete the study according to protocol after recruitment of subjects with valid informed consent.
3. There is no additional risk or safety concern due to the research process to either patient or researcher.
4. There is no potential conflict of interest in this study and an entirely an academic research project.

[figure not shown]
Procedure of maintaining confidentiality

1. For safeguarding confidentiality and protecting anonymity each of the patients will be given a special ID number which will be followed during examination and each and every step of the procedure.
2. A signed informed consent will be taken from the patient convincing that privacy of the patient will be maintained.
3. A data collection sheet will be enclosed for which a short interview will be required.
4. No experimental new drug will be administered.
5. No placebo will be used here.

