3.5 Sampling technique

Simple randomization through lottery in a closed envelope. Randomization number will determine who will receive aspirin & who will not receive aspirin.

2.6 Study Procedure :

This Randomized clinical trial will be conducted in BIRDEM-II. Approval from Institutional Review Board will be taken. The study population will be pregnant women with risk factors for developing PE attending department of Obstetrics and Gynecology, BIRDEM-II. Pregnancy will be confirmed via USG. Then evaluation of risk factors of PE will be done by history taking, examinations & provided investigations. Those who will be eligible according to inclusion & exclusion criteria will be enrolled in the study. Trial information will be provided verbally & with a written information sheet. Participants will be randomized by lottery in a closed envelope, which will determine who receive aspirin daily & who will not. A total of 200 women will be included in the study, of whom 100 pregnant women having risk factors of developing pre-eclampsia will be in experimental group & another 100 pregnant women having risk factors for developing PE will be in control group. Experimental group will be prescribed to take 75 mg Aspirin daily after lunch from 12-19 weeks of pregnancy. Control group will not be prescribed to take Aspirin. For each and every subject separate data collection sheet will be prepared. Data will be collected from the patients using the structured design by history, clinical examination, urine & haematological investigations, USG of the patients. Both group of patients will get the usual advices & medications of pregnancy. All patients will be followed up at 19-24 weeks, 32-34 weeks of gestation, 36 weeks of gestation and weekly up to delivery. During follow up SBP & DBP will be carefully measured. Urine analysis will be done. Aspirin will be stopped either 36 weeks of pregnancy or when delivery occurs or when PE is diagnosed. Primary & Secondary outcome will be observed in both experimental & control group separately. Then analysis will be done by comparison of outcome of this two groups. Data will be analyzed using SPSS software.

2.7 Sample size determination:

Sample size is calculated using the following formula

$$n = \left[\frac{Z_{\alpha} \sqrt{p_1(1-p_1)} + Z_{\beta} \sqrt{p_2(1-p_2)}}{p_2 - p_1} \right]^2$$

Here, n= sample size

$p_1 = 1.6\%$ [Incidence of preeclampsia in experimental group (Rolnik et al., 2017)]

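### The only stated analysis population is women who complete the study per protocol; this drops randomised women and can bias the comparison in either direction

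*Protocol*

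**What the plan says.** The analysis set appears in the list of ethical issues in section 2.16, item 2: "The data analysis will be completed on the subjects who complete the study according to protocol". The sentence goes on to refer to recruitment with valid consent. The same section states "No placebo will be used here" and grants "the right of the participants to withdraw themselves from the research at any time, for any reason".

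Section 2.13 (Data presentation and analysis plan) names the t-test, the chi-square test and the relative risk with its 95% confidence interval, but no population. Section 2.6 (Study Procedure) says only "Then analysis will be done by comparison of outcome of this two groups", which neither restricts nor widens the set.

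Two other statements in section 2.6 bear on who would count as a completer. The visit schedule is common to both arms: "All patients will be followed up at 19-24 weeks, 32-34 weeks of gestation, 36 weeks of gestation and weekly up to delivery". Stopping treatment at the primary event is part of the plan: "Aspirin will be stopped either 36 weeks of pregnancy or when delivery occurs or when PE is diagnosed".

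**The concern.** Randomisation makes the two groups comparable at entry. An analysis limited to those who finish as planned selects on what happens afterwards, and comparability is no longer assured. Three features of this trial make unequal selection plausible:

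- Only the aspirin arm has a tablet to take, or fail to take, for months.
- There is no placebo, so women and staff know the allocation when someone stops, defaults or is judged off protocol.
- The visible data collection sheet in the Appendices has no field for tablets taken. Nothing recorded there would decide who finished according to protocol, and the judgement could be made with allocation and outcome known.

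The primary comparison itself is at stake. At the control rate assumed in section 2.7, 100 women per arm yield about 9 cases (100 × 0.0871 = 8.7), so losing two or three cases from one arm would visibly move the relative risk.

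**Working it through.** **Inputs from section 2.7.** p1 = 1.6% (aspirin), p2 = 8.71% (control), Z = 1.96 and 0.84, 150 per group calculated, 100 per group to be taken. The protocol states no dropout, default or non-adherence rate, so every exclusion figure below is an assumption.

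**1. The plan's own figure.** With pbar = 0.05155 and d = 0.0711, the pooled-variance formula is

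n = [1.96 √(2 pbar(1 − pbar)) + 0.84 √(p1(1 − p1) + p2(1 − p2))]² / d² = (0.6129 + 0.2593)² / 0.005055 = 150.5.

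This agrees with the stated 150. The expression as printed in the protocol evaluates to 46.1, so it is not the one that gave 150; that does not affect this point.

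**2. Exclusions from the aspirin arm only, inactive drug.** Let q be the fraction of the aspirin arm excluded and m the risk of excluded women relative to those kept. Controls are all kept. The completer relative risk is then

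RR = 1 / ((1 − q) + q·m).

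| q | m | RR |
|---|---|---|
| 10% | 1.5 | 1/1.05 = 0.95 |
| 20% | 2 | 1/1.20 = 0.83 |
| 20% | 3 | 1/1.40 = 0.71 |
| 30% | 3 | 1/1.60 = 0.63 |

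**3. The opposite direction, still an inactive drug.** Suppose 30% of aspirin women without pre-eclampsia are excluded, and 10% of everyone else. Risk among retained aspirin women is

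0.0871 × 0.9 / (0.0871 × 0.9 + 0.9129 × 0.7) = 0.0784 / 0.7174 = 0.109.

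Retained controls stay at 0.0871, so RR = 0.109 / 0.0871 = 1.25. In this case about 28% of the aspirin arm is excluded (0.0871 × 0.1 + 0.9129 × 0.3 = 0.283), at about 0.28 times the risk of those kept.

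Exclusions from the control arm act in the same direction. If 20% of controls, at twice the risk of the rest, are dropped and nobody else is, RR = 0.8 + 0.2 × 2 = 1.20.

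**4. Effect on the test.** These results come from simulation: 200,000 trials per case, 100 per arm, 8.71% true risk in both arms, chi-square at two-sided 5%, and 10% of all other women excluded.

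| Aspirin women with pre-eclampsia excluded | RR | Chance of a significant false benefit |
|---|---|---|
| 10% (no difference) | 1.00 | 2.5% |
| 20% | 0.90 | 4.0% |
| 30% | 0.79 | 6.3% |
| 40% | 0.69 | 9.8% |

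In the 1.25 case of step 3 the chance of a false benefit falls to 0.7%, while total type I error rises to 7.8%.

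**5. Exclusion unrelated to outcome.** RR stays at 1.00, but information is lost. Power is Φ{[d√n − 0.6129] / 0.3086}:

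- n = 100: (0.7110 − 0.6129)/0.3086 = 0.318, power 62.5%
- n = 90: 0.200, power 57.9%
- n = 80: 0.075, power 53.0%

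**The case against.** The strongest case against the point is that the sentence stands in an ethics list, is tied to valid consent, and may mean no more than women followed to delivery. A statistical analysis plan or the CONSORT diagram, neither visible here, might define another set. The location and the ambiguity are real, but either meaning removes randomised women, and the protocol states this population outright instead of leaving it open.

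Several stronger readings are tempting, and the documents do not support them:

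- *A reader might infer that the bias must favour aspirin.* It need not; step 3 gives 1.20 to 1.25 with an inactive drug.
- *A reader might infer that exclusions fall mainly on the aspirin arm because controls have nothing to deviate from.* A control who takes aspirin deviates, and the Introduction says several bodies recommend it for high-risk women. Missing visits or delivering elsewhere can happen in either arm, since both share one schedule. Only stopping the tablet is specific to one arm.
- *A reader might infer that developing pre-eclampsia makes a woman a non-completer.* Stopping at diagnosis is part of the plan, so it does not.
- *A reader might infer that the bias matches the effects cited.* The mild case, 0.95, is weaker than either overall relative risk quoted in section 1.5 (0.68 and 0.90), and the planned effect is far stronger (1.6/8.71 = 0.18). The protocol gives no basis for choosing a case.

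It can also be argued that section 1.3 asks what aspirin does when taken. Even so, comparing the women who remain does not answer that without bias unless exclusion is unrelated to risk.

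**Conclusion.** The point holds in a limited form. The protocol fixes a completer analysis as its only stated population, and that rule can bias the randomised comparison. Neither direction nor size can be determined from the document. The illustrative range of 0.95 to 0.63 rests on an inactive drug, no control exclusions, 10-30% of the aspirin arm excluded and a risk multiplier of 1.5 to 3. The 1.25 rests on aspirin women without pre-eclampsia being excluded three times as often as everyone else. At a mild imbalance (20% against 10%) the error rate of the test hardly changes, although the estimate has already moved to 0.90. The loss of power needs no assumption about direction: at the planned rates, even exclusion of 20% takes it from about 62% to 53%. Because the rule governs the primary comparison and is easy to replace, it should be changed before analysis.

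**What to change.** Replace item 2 of section 2.16, preferably moving it to section 2.13, with: *The primary analysis includes all randomised women in the group to which they were allocated, whatever aspirin they took; the completer or per-protocol analysis is a secondary sensitivity analysis.* Consent before randomisation is a condition of entry and should not be used to define the analysis set afterwards.

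State that the follow-up to delivery already planned for all patients also applies to women who stop aspirin. Report a sensitivity analysis for women whose outcome is unknown. If the secondary completer analysis is kept, define what completing according to protocol means in each arm and record it.

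The cost is a change of wording, a little extra tracing of defaulters (the data sheet already collects a contact number), and some dilution of the estimated effect by non-adherence.
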